#### H. Chart Review and Database Extraction

1. Therapy Attendance and Service Use Outcomes. Episodes reflecting use of VA substance abuse, specialized PTSD and other mental health treatment will be collected from VA administrative records as described previously (Harpaz-Rotem, Rosenheck et al. 2009). The investigators have extensive experience analyzing VA service use data. [name] is a national authority on service use analyses.

The Austin Information Technology Center provides the service use data for [name] analyses. The Austin databases hold data from all Veterans who received any services from anywhere in VA. The Patient Treatment File contains all episodes of inpatient care delivered within the VA system. The Outpatient Encounter File documents all outpatient VA service use. VA bed section codes indicate hospitalization on specialized units and VA clinic codes indicate outpatient treatment in specialized clinics. In a recent manuscript, [name] describes analysis of psychotherapy service use codes from these databases (Hunt and Rosenheck, 2011), which will be extracted as psychotherapy participation may reflect a more specific measure of engagement in treatment than broader measures.

Service use data will be collected from three months before the Compensation claim was filed until three months after claims adjudication. We will also collect the date Veteran was separated from military service to determine when VA services became available to each Veteran.

2. Compensation examinations of each Veteran will be reviewed by research assistants who will complete a chart extraction form. The extraction form collates the following information:

- i. Clinician diagnosis from C&P exam
- ii. Alcohol Use

-- Level of detail describing alcohol use (No mention, Impression but no number of drinks, or number of drinks---including a statement that there has been no recent use).

- Amount of alcohol reported used in drinks/drinking day
- Alcohol Use Consequence (no mention, consequences listed)
- Alcohol Use Disorder Diagnosed (no diagnosis; use noted but no judgment that it is a problem, or merits intervention; rule-out alcohol use diagnosis made; alcohol use diagnosis made)

iii. Other Substance Use (characterized as for alcohol, with delineation of particular drugs)

3. Award determination by VBA: Award determination will also be the dependent measure in proposed secondary analyses. The data collected will be whether any benefit was awarded, and the percentage service connection awarded.

4. The VA databases will be used to identify all non-exclusive psychiatric diagnoses, as defined in the DSM-IV and DSM-V, ICD 9 and ICD 10.

5. Distance from VA: Veterans' addresses collected upon enrollment will be converted into distance from the nearest VA facility using Global Information System (G.I.S.) mapping (Fortney 2000). Participants and VA treatment facilities will be geocoded by street level (the G.I.S. will use the street address) to calculate driving distance as a measure of treatment accessibility. Distance from treatment has been associated with receipt of fewer services (Rost, Fortney et al. 2002).

6. Chart review to determine presence of a substance abuse disorder at time of Compensation.

#### I. Measures Collected from Therapists after SBIRT Counseling Sessions

1. Overview: It is important to measure the fidelity and skill with which SBIRT is delivered, and to measure non-specific but potentially important ingredients such as general supportiveness of the therapist. Each therapists' first eight Veterans treated with SBIRT will be videotaped except if the Veteran asks not be videotaped. Subsequently, a random sample of 10% of sessions will be videotaped and rated. Therapists will set up the recording equipment and sound-amplifying microphone. The camera will be trained on the therapist.

2. Rating of Therapy Videotapes: Videotapes will be rated using ratings drawn from the Yale Adherence and Competence Scale (Carroll et al., 2000) and the current Benefits Counseling study. Standard procedures will be used to rate the videotaped sessions. Two raters blind to the study design will be trained by the P.I. and will rate sessions. During rater training, raters will review the rating form, anchor points, and procedures to rate the sessions. They will then view a videotape, rate it, and review the ratings with the P.I. Discrepancies between the raters will be reviewed and the process will be repeated for successive tapes until adequate inter-rater reliability is achieved. After the two raters have been trained, they will together rate 20% of the collected videotapes.

3. Videotape Rating Scale: Raters will indicate the frequency and extensiveness with which an element of the therapy is covered during a session using a Likert scale anchored by 1- not at all and 7- extensively, with descriptions of what constitutes meeting these anchors. A second scale rates therapist skill level at covering the element (if covered) on a scale anchored by 1- very poor to 7- excellent. The dimensions of adherence and competence are only modestly correlated and thus reflect different aspects of treatment (Carroll, Nich et al. 2000). The subscales and items will determine:

- i. if essential elements of SBIRT were delivered (assessment, feedback, referral)
- ii. use of Motivational Interviewing (empathy, developing discrepancy, rolling with resistance)
- iii. general factors (optimism, discussion about VA, general inquiries)
- iv. proscribed elements (convey value judgments concerning disability, substance use)

4. Time Spent Providing Counseling: A contact log will be completed for each phone or face-to-face encounter, including scheduling. The contact log will document whether there was a scheduled contact that was not attended, the date and time of contact, type of contact (face-to-face, phone, cancelled appointment), and time spent in minutes.

#### J. Data Analysis for Evaluative Component:

1. Sample Analyzed for Evaluative Component: The effects of substance abuse on outcomes will be analyzed in the sample of 560 participants who did not receive SBIRT, 80 of whom report risky alcohol/substance use and 480 who did not.

2. Data Reduction: Substance use disorder, PTSD diagnosis, and treatment attendance measures are being collected from more than one source. It is important to reduce the data prior to subsequent analyses to identify the outcomes that will be used in the analyses. These data reduction approaches are shown below:

a. The presence or absence of an Alcohol Use disorder at the time of the Compensation examination will be determined by the best estimate procedure developed by Spitzer and colleagues for validating DSM diagnoses (Spitzer, 1983). This procedure involves reviewing all available sources of information, which for this measure will include the SCID interview, Compensation examination report, substance use calendar, chart review and ICD-9 diagnoses.

A sensitive definition of alcohol use disorder will be employed, and the Principal Investigator will review all cases for which the Compensation Examination and SCID diagnosis are discordant. The reasons to use a sensitive but possibly less specific definition of alcohol use disorder are that an extensive literature documents that there are few "false positive" reports of alcohol and other substance abuse (Kosten and Rounsaville 1992). In a population of Veterans applying for PTSD-based disability, Veterans drinking substantial amounts of alcohol are likely to meet criteria for either Abuse or Dependence, and people with PTSD are particularly vulnerable to the psychological disruptions caused by drugs of abuse (Back, Brady et al. 2006). The same approach will be taken to arriving at best estimate diagnoses for other substances of abuse. The stability of the results will be determined by substituting alternate definitions of the substance use construct.

Descriptive analyses will be conducted to describe the agreement between the different sources of information. For example, the definition of alcohol-use disorders will be compared between the SCID Diagnoses during the assessment battery and the Compensation examinations. Preliminary descriptive and ROC analyses will be conducted of the accuracy of the Compensation examinations for determining alcohol use disorders with the validating criterion being the best estimate diagnosis.

b. Treatment attendance will be determined from Austin databases and from the self-reported Service Use calendar. Self-report data will be used for outcomes that cannot be determined from the Austin databases---use of non-VA services, and whether substance abuse was addressed during a counseling session.

Because *sustained* attendance has been more strongly associated with benefit from substance abuse treatment than intensity of treatment (Ritsher, McKellar et al. 2002; Moos and Moos 2003), attendance at treatment will be determined as a dichotomous variable on a week-by-week basis. The extent of therapy attendance will be determined separately for three types of treatment: Mental Health in PTSD specialty clinics, Mental Health in non-specialty clinics, and Substance Abuse specialty treatment.

Each category of therapy contacts will be subdivided as treatment with and without psychotherapy, creating six total therapy attendance measures. Analyzing the subset of contacts representing psychotherapy visits will cull for visits that represent willingness to discuss the problem behavior/symptoms. [name] has utilized methods identifying psychotherapy stop codes in the Austin databases in a completed service use analysis (Hunt and Rosenheck, 2011).

c. Exploratory analyses will be conducted concerning the agreement of Compensation examination PTSD diagnoses and CAPS-generated PTSD diagnoses. ROC analyses will be conducted on the accuracy of the Compensation examination diagnoses of PTSD with the

validating criterion being a diagnosis derived from the CAPS interview. The CAPS interview, like the Compensation examination, measures the specific DSM IV criteria for PTSD, so concordance is expected to be high. A diagnosis of PTSD will be derived from the CAPS using the “1/2” rule, in which (1) a core PTSD symptom is counted as present when its frequency is rated as a ‘1’ or greater and its intensity is rated as a ‘2’ or greater; and (2) total CAPS severity  $\geq 45$  (Schnurr, Friedman et al. 2005). This strategy ensures that the DSM-IV symptom criteria are met and that severity is sufficiently high. Exploratory analyses will examine characteristics associated with discordance between Compensation examination and CAPS interview diagnoses (diagnosis on CAPS but not on Compensation examination and vice versa).

3. Approach to Missing Data: We will first determine whether data are missing completely at random using Little’s (1988) test. If data are not missing at random, we will characterize study drop-outs in terms of differences in mean scores on relevant variables. Variables determined to be related to missingness or to the incomplete variables (missing data correlates) will be included in models to improve estimation.

For analyses involving hierarchical linear modeling, maximum likelihood estimation techniques permit missing data on the dependent variable. Valid parameters are estimated from all available data from all cases under the assumption that data are missing at random. To improve the plausibility of the missing-at-random assumption, we may include missing data correlates in the model.

For normal models (ANOVA, Regression), if data are not missing-at-random, we will use NORM software to multiply impute missing values. We will combine parameter estimates and estimate standard errors according to Rubin’s rules (cited in Schafer, 1997).

4. Analysis of the Effect of Substance Use on PTSD, Treatment Attendance (Evaluative Specific Aim 1-- Veterans with substance use disorders randomized to No-Additional-Treatment will have worse PTSD over time compared to Veterans without substance use disorders and will attend fewer weeks of mental health and/or substance abuse treatment):

The principal strategy for assessing the effect of substance use on outcomes (CAPS score, weeks attending any mental health and/or substance abuse treatment) will be random effects regression, also called HLM or hierarchical linear modeling. An individual’s behavior on the outcome variable is modeled as a function of an individual growth trajectory (and thus does not require all participants to have data at all measurement points), and then, at a between participants level, the parameters of the individual trajectories are analyzed by group. The focus of these analyses will be the ‘substance use status by time effects’ for each hypothesis. These effects will evaluate whether the slopes, or rates of change, of one group differ from the slopes of another group. The effects of (site) and (site X substance use) status will be modeled.

Because substance use is not randomly assigned, potentially confounding baseline covariates will be considered in the analyses. Baseline level of the dependent variable, e.g. CAPS-rated PTSD severity, will be included in the analysis as a covariate. Other covariates will be included that have been associated with substance use that also might potentially be associated with the outcomes being studied, i.e. PTSD severity and treatment attendance. The covariates will include gender, education level (years of study), current employment status, depression severity (as assessed by the BDI), response to stressful experiences, and meeting criteria for TBI (as assessed by the baseline questionnaire).

We will also examine the within-subjects relationship between the substance use and PTSD outcomes. We hypothesize that improvements in substance use will correspond with improvements in PTSD as evidenced by a significant positive correlation between the slopes of substance use measures (e.g. abstinence, heavy drinking days) and CAPS scores. We also plan to utilize a Structural Equation Model that has the combined benefits of latent curve, autoregressive, and time-specific lagged effects analyses (Bollen & Curran, 2004). We will

analyze the immediate and lagged effects of substance use on CAPS scores. The same approach will be applied to elucidate the relationship between substance use and treatment attendance. Additionally, we will analyze the nature of the effect of each outcome at the previous time point (time t-1) on the value of the same outcome at the current time point (time t). In this manner, we will determine the unique and combined effects of all influences on PTSD symptoms and treatment attendance.

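### The Compensation exam's accuracy for alcohol use disorder is judged against a best estimate that includes the exam's own report, which pushes apparent specificity toward 100%

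*Combined protocol and SAP*

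**What the plan says.** Section J.2.a (Data Reduction) sets the presence of an alcohol use disorder by a best estimate procedure that reviews all available information, "which for this measure will include the SCID interview, Compensation examination report, substance use calendar, chart review and ICD-9 diagnoses". On how sources are combined it says "A sensitive definition of alcohol use disorder will be employed", arguing that false positive reports are few. No exact combination rule is given. Disagreements go to one person: "the Principal Investigator will review all cases for which the Compensation Examination and SCID diagnosis are discordant". No blinding is stated.

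The section then plans descriptive and ROC analyses of "the accuracy of the Compensation examinations for determining alcohol use disorders with the validating criterion being the best estimate diagnosis".

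Two other provisions bear on this. The definition of alcohol use disorder "will be compared between the SCID Diagnoses during the assessment battery and the Compensation examinations", which is a comparison of agreement. And "The stability of the results will be determined by substituting alternate definitions of the substance use construct"; none of these definitions is named or said to leave out the exam.

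For PTSD, section J.2.c validates the same examination against a CAPS-derived diagnosis alone, a criterion that does not contain the exam.

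**The concern.** An accuracy figure should compare a test with something other than itself. Here a Veteran whom only the exam calls positive can become a case because the exam said so, and the exam is then credited with a correct detection. Part of the reported accuracy would be the exam agreeing with itself.

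The review of discordant cases does not break this loop. Anyone who sees a SCID-negative case flagged as discordant knows that the exam was positive. Chart review and ICD-9 codes may also carry exam content, since Human Subjects section C.1 places exam reports on VA clinical servers. The plan does not say whether such entries are excluded.

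The Background stresses inattention to substance abuse at these examinations, and the Potential Benefits section says results may suggest changes to exam procedures. A near-perfect specificity produced by construction could mislead readers on that question.

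**Working it through.** The plan states no sensitivity, specificity or AUC for this analysis, so there is no figure to reproduce. The check is 2×2 algebra at one cut-point; no effect on the AUC was derived.

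**Set-up.** Cross the exam with the best estimate from the other sources only: A = both positive, B = exam negative and others positive, C = exam positive and others negative, D = both negative. Without the exam, sensitivity is A/(A+B) and specificity is D/(C+D). Let q be the share of cell C accepted as cases once the exam report is included:

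- sensitivity = (A + qC)/(A + B + qC), never below A/(A+B)
- specificity = D/(D + (1−q)C), never below D/(C+D), and exactly 1 when q = 1

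**Inputs.** Assumed exam-free accuracy: Se = .50, Sp = .90. Prevalence p:

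- .25: expected share meeting the substance use criteria (Research Design, section A), a proxy.
- .32: 20/62 in the Connecticut chart review (Feasibility, section B.4.b); includes rule-outs and other substances.
- .475: (.29 − .10)/(.50 − .10), treating that review's 18/62 = .29 as the exam-positive rate. This too is an assumption.

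The values do not share one calibration: at p = .32 the implied exam-positive rate is .50 × .32 + .10 × .68 = .228, not .29.

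**Illustration 1: exam-free reference correct.** At p = .32: A = .160, B = .160, C = .068, D = .612.

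- q = .5: sensitivity .194/.354 = .548; specificity .612/.646 = .947
- q = 1: sensitivity .228/.388 = .588; specificity 1.00

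| p | q = .5 | q = 1 |
|---|---|---|
| .25 | .565 / .947 | .615 / 1.00 |
| .32 | .548 / .947 | .588 / 1.00 |
| .475 | .526 / .947 | .550 / 1.00 |

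Over exam-free sensitivity .40 to .70, specificity .80 to .95 and p = .25 to .32, q = 1 always gives specificity 1.00 and adds about 3 to 22.5 points to sensitivity.

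**Illustration 2: when sensitivity falls.** The extraction form in section H.2 records drinks per drinking day and grades the alcohol finding below a definite diagnosis ("no diagnosis; use noted but no judgment that it is a problem, or merits intervention; rule-out alcohol use diagnosis made"). Section J.2.a also argues that "Veterans drinking substantial amounts of alcohol are likely to meet criteria for either Abuse or Dependence". The report can therefore create cases that the exam did not diagnose, and these count as exam misses. If a share n of cell D becomes cases this way, sensitivity stays above Se only while

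n < q × [(1−Sp)/Sp] × [(1−Se)/Se] = q × (.10/.90) × 1,

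that is, below 11.1% for q = 1 or 5.6% for q = .5, at any prevalence. At n = .10 and q = .5, sensitivity is .194/(.354 + .0612) = .467 at p = .32 and .481 at p = .475. Specificity is .5508/.5848 = .942, still above .90; it rises whenever q > n.

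**Illustration 3: imperfect sources.** True exam accuracy .50/.90; SCID .80/1.00; the other three sources together .90/.80; errors conditionally independent; any positive source makes a case.

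| Reference | p = .32 | p = .475 |
|---|---|---|
| Same sources without the exam | .379 / .895 | .426 / .891 |
| With the exam, q = .5 | .416 / .945 | .449 / .942 |
| With the exam, q = 1 | .450 / 1.00 | .470 / 1.00 |
| SCID alone | .50 / .866 | .50 / .839 |

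Including the exam raises both figures relative to the same sources without it. Sensitivity remains below the SCID-alone value, so the direction does not extend to a comparison with the SCID alone.

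**The case against.** **The stakes are low and partly covered.** The analyses are labelled preliminary, appear in no hypothesis or power statement, and the planned exam-versus-SCID comparison would largely yield accuracy against the SCID. All of this stands and sets the weight. It does not change which criterion is named for the accuracy analysis.

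**Best estimate is meant to use everything.** That is right for classifying Veterans in Aim 1. It does not suit measuring the accuracy of one of the sources.

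**The rise in sensitivity is not assured.** This stands: illustration 2 reverses it at modest values of n, and the documents do not show that n is smaller. Specificity is the robust part.

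**An exam-free criterion may be no nearer the truth.** This is the strongest point. In illustration 3 the true sensitivity + specificity − 1 is .40. The exam-free multi-source reference gives .274 and .317 (p = .32 and .475); the full best estimate gives .361 and .391 at q = .5, and .450 and .470 at q = 1, nearer in every case. If the SCID is .90/.80, the SCID alone gives .372/.878 and .421/.859, while SCID plus exam at q = 1 gives .461/1.00 and .485/1.00, again nearer on that index and on sensitivity. But the gain comes from self-agreement offsetting the other sources' errors, by an amount that depends on an unknown q. On specificity, the exam-free figure is the nearer one in both of these comparisons. Offsetting errors under assumed inputs do not make an index test a valid criterion for itself.

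**Conclusion.** The concern holds. As written, the plan validates the Compensation examination against a diagnosis built partly from that examination. Relative to the same sources without the exam, apparent specificity is pushed toward 100%: from an assumed .90 to about .95 if half the exam-only positives are accepted, and to 1.00 by construction if all are. Apparent sensitivity tends to rise, from an assumed .50 to between .53 and .59 at prevalence .32 to .475, unless narrative data create enough additional cases. Exam accuracy, prevalence and the acceptance share are all assumptions, so these sizes are illustrative; the overlap itself is explicit in section J.2.a. This is a low-weight point: it leaves the primary outcomes and Aim 1 untouched.

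**What to change.** For the exam-accuracy analyses only, name one exam-free criterion in advance. Either option serves:

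- **Baseline SCID diagnosis.** This parallels the use of the CAPS for PTSD. It is already collected at baseline (Schedule of Assessments), on the exam day or up to two weeks before (Single Patient Flow Chart). Cost: one or two sentences and no new data.
- **Exam-free best estimate.** Built without the exam report and without chart notes or ICD-9 codes that come from it, by a reviewer who has not seen the exam result. Cost: a second review of existing records.

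Report accuracy against the full best estimate as a secondary figure, labelled as including the exam, and state which coded exam level counts as positive. Apply the same rule to other substances if their exam accuracy is analysed. Keep the full best estimate for Aim 1.

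The report should also state the limit of the change: an exam-free criterion removes self-agreement, not error in the criterion. With true exam accuracy .50/.90, an SCID at .80/1.00 gives apparent specificity .84 to .87, and an SCID at .90/.80 gives apparent sensitivity .37 to .42.

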## 7. PTSD Assessments

a. The Life Events Checklist (Weathers, Keane et al. 2001) inquires about whether the Veteran has had exposure to each of 17 classes of traumatic events. Veterans will be asked to identify the trauma causing the most current distress. Military sexual trauma will be defined by having had a sexual experience during military service that was unwanted and involved force or threat of force.

b. Clinician Administered PTSD Scale (CAPS): The CAPS is an extensively validated (Forbes, Creamer et al. 2001; Monson, Gradus et al. 2008) clinical interview used to derive a rating of PTSD symptom severity and diagnosis. It consists of 17 ratings of the frequency and severity of PTSD symptoms listed in DSM-IV-TR. Cluster subscales can be derived for the PTSD symptom clusters of hyperarousal, avoidance/numbing, and re-experiencing.

The CAPS takes 45-60 minutes to administer and requires a data collector with clinical experience. The CAPS is widely considered to be the gold standard measure of PTSD severity, and agreement between the CAPS and self-report measures such as the PTSD Checklist–Military has been variable (Monson, Gradus et al. 2008). Only the CAPS is observer-rated. The CAPS is more specific for PTSD than the PTSD Checklist because unlike the Checklist, the CAPS only rates emotional numbing and hyperarousal symptoms if they are not

accounted for by another disorder.

8. Beck Depression Inventory II is the updated iteration of the older Beck Depression Inventory. Respondents rate 21 statements reflecting the previous two weeks. The Beck includes items reflecting DSM IV somatic symptoms of depression and more cognitive factors associated with depression, and is thus well-suited to depression measurement among people with a high prevalence of somatic symptoms related to substance use. It showed excellent receiver-operating characteristics in identifying depressed Veterans from a cohort of Veterans with TBI and frequent comorbid PTSD (Homaifar, Brenner et al. 2009). Depression has been strongly associated with function among people with PTSD (Hoge, McGurk et al. 2008).

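### The PTSD agreement analysis assumes every Compensation examination uses DSM-IV, although the plan expects VA diagnoses under two DSM editions and does not record which edition the examiner used

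*Combined protocol and SAP*

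**What the plan says.** All references are to the combined protocol and SAP.

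- **Section J.2.c (Data Reduction)** introduces the comparison: "Exploratory analyses will be conducted concerning the agreement of Compensation examination PTSD diagnoses and CAPS-generated PTSD diagnoses". The CAPS diagnosis is the validating criterion in an ROC analysis, and a further exploratory analysis looks for characteristics associated with discordance in either direction. The reason given for expecting good agreement is that "The CAPS interview, like the Compensation examination, measures the specific DSM IV criteria for PTSD, so concordance is expected to be high".
- **Section G.7.b (PTSD Assessments)** fixes the CAPS to one edition: "It consists of 17 ratings of the frequency and severity of PTSD symptoms listed in DSM-IV-TR". Section J.2.c derives the diagnosis from those items and adds a total severity of at least 45.
- **Section H.4 (Chart Review and Database Extraction)** expects more than one edition in VA data: "The VA databases will be used to identify all non-exclusive psychiatric diagnoses, as defined in the DSM-IV and DSM-V, ICD 9 and ICD 10".
- **Section H.2** lists what is taken from each examination report. For diagnosis the item is "Clinician diagnosis from C&P exam". Neither the DSM edition nor the examination date is among the items.
- **Section J.2.a** concerns a different construct, the best-estimate diagnosis of alcohol and other substance use disorders. Its named sources are "the SCID interview, Compensation examination report, substance use calendar, chart review and ICD-9 diagnoses".

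**The concern.** The expectation of high concordance depends on both diagnoses answering the same question. That is secure for the CAPS, which is a DSM-IV instrument throughout. For the examinations it is only asserted, in a plan that elsewhere expects DSM-IV and DSM-V diagnoses side by side in VA data.

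If some examiners apply the newer edition, a correct diagnosis under their criteria can disagree with the CAPS simply because the definitions differ. The ROC analysis would then count a difference of definition as examiner inaccuracy. The discordance analysis is exposed in a second way: edition would follow calendar time, so any characteristic that also follows examination date (enrolment period, for instance, or site if the sites changed at different times) could appear to predict discordance. With no edition field, the data as planned would not show whether the premise held.

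**Working it through.** **Step 1. Is there a figure to reproduce?** No. The plan states no target or expected value for kappa, sensitivity, specificity or area under the ROC curve. The check is a comparison of sections, followed by an illustration.

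**Step 2. The sections side by side.**

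| Item | Section | Edition |
|---|---|---|
| CAPS criterion | G.7.b, J.2.c | DSM-IV only |
| Compensation examination | J.2.c | Taken to be DSM-IV |
| Compensation examination as extracted | H.2 | Not recorded |
| VA database diagnoses | H.4 | DSM-IV and DSM-V |
| Split or adjustment by edition or date in the PTSD agreement analysis | J.2.c | None stated |
| Recruitment period | B.4.c | Three years |

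The H.4 row and the J.2.c premise are never reconciled. Section J.2.a plans to substitute alternate definitions of the substance use construct; no such check is planned for the PTSD diagnosis.

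**Step 3. Illustration: symmetric disagreement between editions.** All inputs in this step are assumptions, not figures from the documents. Suppose an examiner has sensitivity .85 and specificity .85 against the edition he or she applies. Suppose also that the two editions agree in a share *a* of cases, equally among CAPS-positive and CAPS-negative Veterans, and that examiner error is independent of edition disagreement. Then

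- sensitivity against the DSM-IV CAPS, newer-edition examinations: .85a + .15(1 − a)
- pooled sensitivity when a share *f* of examinations use the newer edition: f × (that value) + (1 − f) × .85

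| a | Newer-edition examinations | Pooled, f = .5 |
|---|---|---|
| 1.00 | .85 | .85 |
| .95 | .8075 + .0075 = .815 | .8325 |
| .90 | .765 + .015 = .78 | .815 |
| .85 | .7225 + .0225 = .745 | .7975 |

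**Step 4. The same idea on the kappa scale.** Take CAPS prevalence as .61, borrowed from the share of Compensation examinations with a PTSD diagnosis in the Connecticut chart review (section B.4.b). Assume sensitivity = specificity = .90 and symmetric reclassification of a share r.

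- r = 0: observed agreement .90. Share diagnosed at examination = .61 × .90 + .39 × .10 = .588. Chance agreement = .61 × .588 + .39 × .412 = .519. Kappa = (.90 − .519)/(1 − .519) = 0.79, whatever the share under the newer edition.
- r = 10%, all examinations under the newer edition: sensitivity = specificity = .90 × .90 + .10 × .10 = .82, and kappa = 0.63. At a half share kappa = 0.71.
- r = 5%: kappa = 0.71 for all examinations, 0.75 at a half share.

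Starting from sensitivity = specificity = .80, kappa is 0.59 with no reclassification and 0.47 with r = 10% and all examinations under the newer edition.

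**Step 5. The direction is not fixed.** Steps 3 and 4 force both measures down by assuming symmetry. Suppose instead that the newer criteria, as applied, turn 10% of examination negatives into positives and change nothing else. Sensitivity becomes .85 + .10 × .15 = .865 and specificity becomes .85 × .90 = .765. If they turn 10% of positives into negatives, the two values change places. Sensitivity and specificity can therefore move in opposite directions.

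**The case against.** The strongest reply is that section H.4 concerns diagnoses in VA databases, not the criteria that Compensation examiners apply. Service use data run to three months after adjudication (section H.1), so the databases could span two editions even if the examinations did not. The only statement about examiners is the one in section J.2.c, and it says DSM-IV. This stands. A reader might infer that agreement must drift with calendar time as a matter of design; the documents do not support that, because they give no examiner edition and no changeover date. The point is conditional.

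A reader might also infer that examiner accuracy will appear to fall. Step 5 shows that this does not follow. The severity threshold of 45 in the CAPS rule is, moreover, a source of discordance unrelated to edition.

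Thirdly, a reader might take section J.2.a to mean that the best estimate uses ICD-9 codes and nothing else, so that it fails for Veterans coded under ICD-10. It does not say so. ICD-9 is one of five named sources in a review of all available information, section H.4 already collects ICD-10 codes, and the Principal Investigator reviews every case where the SCID and the examination disagree. The best estimate also concerns substance use disorders, so its wording has no bearing on PTSD agreement.

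Finally, the PTSD agreement and discordance analyses are labelled exploratory, and the design already needs the timing of the examination (section J.6 uses it as a time-varying covariate), so a check by period needs no redesign. Both points are right. They lower the importance of the concern and the cost of acting on it, but they do not supply the missing edition field or the missing split.

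**Conclusion.** The concern holds in conditional form. The plan expects two DSM editions in VA diagnoses but treats every Compensation examination as DSM-IV, and it provides no means of checking. If some examiners use the newer edition during recruitment, differences of definition may be reported as examiner error and correlates of examination date may appear as predictors of discordance.

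The size and direction cannot be determined from the documents. The illustrations range from no change (editions fully concordant) to a pooled sensitivity near .80 instead of .85, or a kappa of 0.63 instead of 0.79. They rest on assumed examiner accuracy, assumed agreement between editions, an assumed share of examinations under the newer edition, and independence of the two sources of error.

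Importance is low. The co-primary trial outcomes in section K.1 (days using any substance and weeks attending treatment) do not depend on this analysis, and neither does the CAPS score as a secondary outcome. It merits a change because the change costs very little. The ICD-9 wording in section J.2.a is a separate clarification only.

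**What to change.** 1. **Section H.2:** add to the extraction form the DSM edition used in the examination or, where the report does not state it, the examination date.
2. **Section J.2.c:** report sensitivity, specificity and ROC results by edition (or by period, with the cut fixed before agreement is examined) alongside the pooled result. Replace the premise that all examinations use DSM-IV with a statement that this will be checked.
3. **Section J.2.c, discordance analysis:** include edition or period as a covariate.
4. **Section J.2.a, separate minor clarification:** change the coded source from ICD-9 diagnoses to ICD-9 or ICD-10 diagnoses, to match section H.4.

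The cost is one extraction field and a few lines of text. The downside is that edition-specific estimates use fewer examinations and are less precise. Where only the date is available, period is a proxy: a difference between periods may reflect other changes over time and should not be read as an edition effect without qualification.
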